The studies will be conducted at UVA and will require IRB approval prior to the initiation of the trial. Thirty-six subjects with Type 1 Diabetes Mellitus will be needed to complete the protocol.

Based on our experience with similar studies, we estimate an expected 20-30% screen failures, dropouts, or withdrawals (7 to 10 subjects at UVA); thus we intend to set a recruiting target of 45 subjects. One pilot subject will be enrolled to test system performance. More than one subject may be admitted at one time.

Specific Aim 1 (SA1): Hypoglycemic risk, Open vs. Closed Loop (exercise)

Specific Aim 2 (SA2): Time within target range, Open vs. Closed Loop control during the day

Specific Aim 3 (SA3): Time within target range at night

Specific Aim 4 (Substudy/exploratory): Assess the effect size of Control Modules 1+3 (SSM+BRM) preventing nocturnal hypoglycemia and increasing time within target (80-140mg/dl) overnight as compared to CGM-augmented pump alone.

The testing of the three specific aims of the main study (SA1, SA2, SA3) involves different periods of time as presented in Figure 3. Thus, in addition to complete data, availability of partial data would allow testing some of the study hypotheses. As a general rule, a session will be considered useful for data analysis if the subject completes more than 80% of the active study protocol (29 out of 36 hours for the experimental session). Sessions completing less than 80% of the protocol will be rescheduled. Specifically, comparing risk and occurrence of hypoglycemia during the 5-hour periods encompassing exercise (14:00-19:00) on open- vs. closed-loop control will address SA1. Comparing the time within target range (70-180mg/dl) during the day (7:00-23:00) on open- vs. advisory control will address SA2, and comparing the time within target range (80-140mg/dl) and the risk for hypoglycemia overnight will address SA3 (Figure 2).

To determine sample size we used power analysis based on data from our previous closed-loop control studies, which showed significant reduction in hypoglycemia (due to Module 1) and increase in time within target during the day and overnight [15]. With N=36 subjects, the power for proving SA1 is 97% and the power for SA3 is similar, while the power for SA2 is lower, but sufficient - 85%. The significance level was reduced to $p=0.01$ to account for multiple comparisons.

[figure not shown]

Figure 2: Experimental vs. Control sessions

D. Study Duration

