 - Study personnel with direct subject contact are required to complete Blood borne Pathogens and Infection Control training annually.

Medical Personnel Training

All study nurses will be currently licensed RNs. All RNs that are employed by the study are oriented to the care of the T1D research subject. Certification of their skill level is supervised by the study Nurse Manager. Other medical personnel may be licensed Emergency Medical Technicians. All medical personnel who will have direct contact with the study subject have current certification in Basic Life Support including CPR and AED. Study physicians will be available during the trial.

I. STOPPING RULES

Entire study

The study will be stopped if three similar AE's occur that are deemed moderate or severe or if there is system communication failures, which may trigger revision of the system software. Additionally, the Principal Investigator, IRB-HSR, Safety Officer, or sponsor may decide to stop the trial or part of the trial at any time. In this case, the Principal Investigator will promptly inform the subjects and assure appropriate therapy and follow-up. Additionally the Principal Investigator will notify the IRB if the study is temporarily stopped. The pertinent regulatory authorities will be informed according to national regulations.

Early study stop will be documented and following information will be collected:

- Date and cause of the ending

- Description of any serious adverse event leading to the study ending

A subject who does not complete the protocol may be replaced or rescheduled. Available data will be exploited.

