In the case of an unanticipated adverse device effects (UADE), the overall study may be suspended while the problem is diagnosed and the PI investigates the UADE. If the PI determines that the UADE poses an unreasonable risk to subjects, the study should be suspended until this UADE can be resolved. If it cannot be resolved, the study should be terminated. Termination should occur no later than 5 working days after PI makes the decision. The result of the investigation and the PI's decision to terminate the study shall be reported the site IRB, and the FDA per 21CFR 812.46(b) (2). The medical monitor must determine if the UADE presents an unreasonable risk to subjects. If so, the medical monitor must ensure that all investigations, or parts of investigations presenting that risk, are terminated as soon as possible but no later than 5 working days after the medical monitor makes this determination and no later than 15 working days after first receipt notice of the UADE.

The study may resume if the underlying problem can be corrected by a protocol or system modification that will not invalidate the results obtained prior to suspension. The IRB will be notified if the study is stopped, and permission to resume will be obtained from the FDA and IRB prior to restarting.

SUBJECT WITHDRAWAL CRITERIA

An individual subject can be stopped from study participation at subject, PI, study MD, or sponsor's request.

The Principal Investigator, IRB-HSR, or Safety Officer may decide to stop the trial or part of the trial at any time. In this case, the Study MD will promptly inform the subject and assure appropriate therapy and follow-up. Additionally, the Principal Investigator will promptly inform the IRB and provide a detailed written explanation. The pertinent regulatory authorities will be informed according to national regulations.

The subject may request to be withdrawn from the study at any time for any/no reason. A subject will be withdrawn at the subject's request (withdrawal of informed consent) or at the request of the PI or sponsor.

Study procedures other than those required for subject safety would be stopped if:

- The subject had a serious adverse event deemed related to study.
- Glucagon is required to treat hypoglycemia.
- The subject experiences a hypoglycemic seizure.
- The subject becomes unconscious due to hypoglycemia.
- SMBG <45 mg/dL at any time during the experimental session

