- SMBG >300 mg/dL for more than 2 hours during the experimental session
- SMBG \geq 400 mg/dL at any time during the experimental session
- The subject develops emesis, nausea and abdominal pain during the experimental session.
- Confirmed β -ketone level \geq 0.6 mmol/L for more than 2 hours during the experimental session
- Confirmed β -ketone level >1.5 mmol/L at any time

- System is in 'Stopped Mode' for more than 2 consecutive hours during the experimental sessions
- The subject has a positive pregnancy test.

Subjects who were not able to complete the study for reasons other than a serious adverse event (i.e. hypoglycemic seizure, etc.) will be permitted to repeat the session.

Reason Study Stopped	Repeat Session?
Equipment Failure or similarly related issues that invalidate study data	Can repeat session
Hyperglycemic Events that did not result in Serious Adverse Event	Can repeat session
Hypoglycemic Events that did not result in Serious Adverse Event	Can repeat session
PI initiated discontinuation of study due to patient or equipment concerns	Can repeat session
Serious or unanticipated adverse event deemed related to the study	Unable to repeat session

Table 1: Repeat Session Table

CATASTROPHIC EVENT PLAN

The Outpatient Emergency Plan will go into effect should a catastrophic event occur during the experimental session. A catastrophic event is defined as any event that requires emergency treatment by medical professionals that exceed the expected parameters of the protocol. A copy of this plan will be located at the monitoring desk. Staff will be aware of its location at all times.

Event	RN Response	Tech Response
Respiratory Arrest	1) Tell Tech to call 911 2) Begin Basic Life Support	Refer to Study Physician on-site
Cardiac Arrest	1) Tell Tech to call 911 2) Begin Basic Life Support	Refer to Study Physician on-site
Severe Hypoglycemic Event as defined by hypoglycemia accompanied by unconsciousness or seizure	1) Tell Tech to call 911 2) Administer glucagon IM (described in Hypoglycemia Safety	Refer to Study Physician on-site
Severe Hyperglycemic Event as defined by β -ketone level ≥ 0.6 mmol/L for >2 hours or >1.5 mmol/L, or symptoms of vomiting or abdominal pain are present	1) Discuss correction dose of insulin to administer s.c. via syringe with study M.D. 2) Encourage p.o. water intake	Refer to Study Physician on-site

Table 2: Outpatient Emergency Plan

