The specific aim SA4 of the Substudy is exploratory – no significant results are expected, but we will assess the effect size of Control Modules 1+3 (SSM+BRM) preventing nocturnal hypoglycemia and increasing time within target (80-140mg/dl) overnight as compared to CGM-augmented pump alone.

K. SUCCESS CRITERIA / GOAL

We hypothesize that, compared to CGM-augmented insulin pump treatment, AAA control will result in moderate effect size of approximately 0.3-0.5 in terms of:

- Prevention of hypoglycemia during and following exercise more efficiently than state-of-the-art care based on CGM and insulin pump;
- Increased time within the target range of 70-180 mg/dl during the day;
- Prevention of nocturnal hypoglycemia and increase of the time within target range (80-140mg/dl) overnight.

As a general rule, a session will be considered useful for data analysis if the subject completes more than 80% of the active study protocol (29 out of 36 hours for the experimental session). Sessions completing less than 80% of the protocol will be rescheduled.

L. STATISTICAL ANALYSIS PLAN

The testing of the three specific aims of the main study involves different periods of time as presented in Figure 2. Thus, in addition to complete data, availability of partial data would allow testing some of the study hypotheses. Measures of time within target range, risk and occurrence of hypoglycemia, glucose variability and system stability will be computed as previously described and will be accompanied by appropriate plots [20]. Repeated measures ANOVA with contrasts will be used to compare the different study periods on the basis of these measures. Specifically:

- Comparing risk and occurrence of hypoglycemia during the 5-hour periods encompassing exercise (14:00-19:00) on open- vs. closed-loop control will address SA1;
- Comparing the time within target range (70-180mg/dl) during the day (7:00-23:00) on open- vs. advisory control will address SA2, and
- Comparing the time within target range (80-140mg/dl) and the risk for hypoglycemia overnight will address SA3 (see Figure 2).

II. INFORMED CONSENT

The Pilot Consent, the Informed Consent, and the Care Partner Consent are presented in Appendix A-8.

III. PATIENT CASE REPORT FORMS

Patient Case Report Forms are presented in Appendix A-9.

IV. INVESTIGATOR AGREEMENT FORMS

Investigators Agreements Forms are presented in Appendix A-10.

V. MONITORING INFORMATION

Data and Safety Monitoring Plan

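### Glucose stops apply only to the experimental session, and the 80% rule then replaces most stopped sessions, so AAA sessions can be re-run because of their outcome

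*Combined protocol and SAP*

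**What the plan says.** **Stops.** Section I.I (Subject Withdrawal Criteria) ends study procedures for "SMBG <45 mg/dL at any time during the experimental session", for "SMBG >300 mg/dL for more than 2 hours during the experimental session", and for a fingerstick at or above "400 mg/dL at any time during the experimental session". Each names the experimental session only.

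**Repeats.** Table 1 allows a repeat after "Hypoglycemic Events that did not result in Serious Adverse Event", and has a matching row for hyperglycaemic events.

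**Which sessions count.** Sections I.C and I.K state, as a general rule, that "a session will be considered useful for data analysis if the subject completes more than 80% of the active study protocol", given as 29 of 36 hours for the experimental session. Then: "Sessions completing less than 80% of the protocol will be rescheduled".

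**Control session.** Section I.G.5 has the participant follow a similar home safety protocol, placed in Appendix A-6, which is not in the supplied text. No fingerstick level that ends the control session appears.

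**Text pointing the other way.** Sections I.C and I.L say that partial data could serve some hypotheses, because the aims use different periods. Section I.I (Stopping Rules) says of participants who do not complete: "Available data will be exploited". Nothing states whether a stopped first attempt or its repeat is analysed.

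**The concern.** The primary endpoints in section I.J are the Low BG Index around exercise, daytime time in range, and overnight hypoglycaemia risk and time in range. The stops are triggered by the same underlying quantity, glucose. If a stopped AAA session is replaced by a fresh attempt while a control session with the same glucose stays in, the two arms of the crossover are selected differently, and the selection depends on the outcome. The data are meant to support regulatory approval and to estimate an effect size, so a tilt in the estimate matters even where the test is little affected.

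The adverse-event record may not make up for this. Section V.H records only events that are both related and serious, so a non-serious glucose stop need not appear there.

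**Working it through.** **1. Reproduce the cut-off.** AAA control runs from 19:00 on Day 5 to 07:00 on Day 7, which is 36 h. 0.80 × 36 = 28.8 h. 28/36 = 77.8% and 29/36 = 80.6%, so the plan's figure of 29 hours is right. 19:00 on Day 5 plus 29 h is 00:00 on Day 7.

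**2. Place the endpoint windows on that clock.**

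| Window | Clock time | Hours | Share before hour 29 |
|---|---|---|---|
| Night 1 (SA3) | 23:00 Day 5 to 07:00 Day 6 | 4–12 | all |
| Day (SA2) | 07:00–23:00 Day 6 | 12–28 | all |
| Exercise (SA1) | 14:00–19:00 Day 6 | 19–24 | all |
| Night 2 (SA3) | 23:00 Day 6 to 07:00 Day 7 | 28–36 | 1/8 |

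A stop in night 1, the SA2 day or the SA1 window therefore always leaves the session short of 29 hours. Only a stop in the last 7 of the 8 hours of night 2 leaves it usable.

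The rule also fits the windows poorly. A session ending at 23:00 on Day 6 (28 h) holds all of SA1, all of SA2 and one full night, yet is rescheduled. One ending at midnight passes with 7 of 8 hours of night 2 missing.

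**3. Size on a skewed index.** The documents give no stop rate, so every rate here is an assumption. Model: N = 36 pairs, no true effect, lognormal index, within-subject correlation 0.5. The 10% of experimental sessions (36 × 0.10 = 3.6 expected) with the highest value of a stop variable are re-drawn once; control sessions never are. Paired t-test, two-sided 0.01, 20,000 trials. The correlation between the stop variable and the endpoint is varied, because a fingerstick at any time in 36 h is not the same as a 5-hour or 16-hour CGM summary.

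| Log-SD | Stop–endpoint correlation | False reduction in mean | Rejection rate at 0.01 |
|---|---|---|---|
| 0.5 | 0.3 | 1.6% | 0.9% |
| 0.5 | 0.5 | 2.8% | 1.1% |
| 0.5 | 1 | 6.6% | 2.6% |
| 1 | 0.3 | 3.1% | 0.6% |
| 1 | 0.5 | 6.5% | 0.6% |
| 1 | 1 | 17.2% | 1.7% |

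When stops are unrelated to the endpoint, the rejection rate is 0.9% (log-SD 0.5) or 0.5% (log-SD 1), so part of the table shows no inflation.

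**4. Size on a normal endpoint, stops tracking it perfectly.** Same N and test, 40,000 trials, correlation 0.5, one re-run. The nominal rate for a false finding that AAA is better is 0.5%.

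| Stopped | Shift toward AAA | False finding for AAA |
|---|---|---|
| 2% | 0.02 SD | 0.8% |
| 5% | 0.05 SD | 1.1% |
| 10% | 0.09 SD | 2.0% |
| 20% | 0.14 SD | 4.0% |

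With zero within-subject correlation and re-runs repeated until a session completes, 10% stopped gives 0.20 SD and 3.9%. These are upper figures, since perfect tracking is unrealistic. For scale, section I.K hypothesises an effect size of 0.3 to 0.5.

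**The case against.** A reader might infer four stronger things, and the documents do not support them.

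- **That stopped data are certainly discarded.** The text says such sessions are rescheduled or may be repeated. The 80% rule is only a general rule, and two other statements favour using what was collected. This is a conflict with no stated resolution. It does not clear the plan: the 80% rule is the only explicit criterion for an analysable session, and choosing between attempts after seeing the data is a risk in itself.
- **That control sessions cannot be stopped.** Glucagon use, seizure, unconsciousness, a related serious event and ketones above 1.5 mmol/L carry no limit to the experimental session. Appendix A-6 is not supplied, so a control stop there cannot be ruled out. The asymmetry in the supplied text is in the fingerstick thresholds and a few other experimental-only items.
- **That every primary endpoint is biased toward AAA.** Replacing a session stopped for hyperglycaemia may remove a low Low BG Index, which works against AAA on that measure. Stops from hour 29 on do not fail the rule.
- **That the false benefit is large.** Figures near the top of the range need stops to coincide with the worst endpoint values. A stop at 03:00 says little about 14:00–19:00. Sessions are staffed, with fingersticks when CGM falls below 90 mg/dL, so stops may be rare.

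One obvious remedy also draws a fair objection. If the unobserved remainder of a stopped AAA window is scored as out of range while a control participant with the same reading continues and recovers, the bias can reverse. With 10% stopped halfway through SA2 and an assumed usual time in range of 70%, the penalty is 0.10 × 0.5 × 70 = 3.5 percentage points against AAA under no true effect. That objection stands and shapes the fix.

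**Conclusion.** The concern holds in limited form. Read under its general rule, the plan replaces an AAA session stopped for glucose before 00:00 on Day 7, and the supplied text has no matching fingerstick stop for control. The likely direction favours AAA on time in range and, for low-glucose stops, on the Low BG Index. For hyperglycaemia stops the direction on the Low BG Index may be the opposite.

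The size cannot be derived from the documents. At an assumed 10% stopped, with one re-run, log-SD 0.5 to 1, stop–endpoint correlation 0.3 to 1 and within-subject correlation 0.5, the false reduction is roughly 1.5% to 17%. Type I error at 0.01 runs from no inflation to roughly 2% (2.6% in the highest case). It is less if stops are rarer. The effect estimate is more clearly exposed than the test. The remedy is cheap before data are analysed and hard to apply afterwards.

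**What to change.** In section I.L, and with sections I.C, I.I and I.K reconciled to it:

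1. Make the first attempt in each arm the primary data, using each window (SA1, SA2, each night of SA3) as observed up to any stop.
2. Replace the session-level 80% rule with a per-window CGM rule applied equally to both arms. At one reading per 5 minutes, 80% is 48 of 60 for SA1 (0.80 × 60), 154 of 192 for SA2 (153.6 rounded up) and 77 of 96 per night (76.8 rounded up). Keep a window cut short by a glucose stop, with its observed data; do not exclude it as incomplete.
3. Let a re-run replace data only after equipment failure unrelated to glucose. Treat a window not yet begun at the stop as missing in the primary mixed or repeated-measures analysis, and use its re-run in a sensitivity analysis.
4. Score the unobserved remainder of stopped windows as out of range or worst rank in a sensitivity analysis only.
5. Report stops and repeats by arm, with the reason.

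**Cost.** This is SAP wording, plus a few partial or missing windows. Some aims may have slightly fewer than 36 pairs. The estimate may be slightly less favourable to AAA, partly because a window cut at its extreme lacks the recovery that a control window would show; the sensitivity analyses should be read beside it. Clinical stopping thresholds, and the option to repeat a session, are unchanged.

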16. The study team will discuss with the subject their usual meal content and methods for estimating carbohydrates. Users will be asked to define a small, medium and large carbohydrate meal as well as provide us with their perception of whether a particular meal will result in slow, medium or fast rise in glucose. Subjects will be provided with Figure 3 below. This will correspond with the meal grid presented to them in the DiAs during the 2-day experimental session.

The closed loop control algorithm will be informed based on the way the subjects make judgments about their meals. Subjects will estimate their meal carbohydrates to determine their meal bolus. To this end, subjects will be asked to define their pre-meal bolus after assessing *their perception* of their meal size and glycemic effect of the meal. To assist subjects, they will be provided the following definition of glycemic effect:

There are two aspects of how food raises the blood sugar – how high the blood sugar goes up and how quickly the blood sugar goes up. For instance, some foods may raise the blood sugar quickly, but not increase the blood sugar very

much. Other foods may increase the blood sugar slowly but will eventually increase the blood sugar to a high final level. We want you to rate both how high you think the blood sugar will increase, and how quickly it will increase after you eat each meal and snack.

[figure not shown]

Figure 3: Hyperglycemic Grid

17. The outpatient visit will last approximately 1 – 3 hours depending on prior knowledge of the devices.
18. The subject will be given an instruction sheet with 24-hour contact information of the research team to address any problems or questions.
19. Unlimited additional appointments and telephone calls to the study team and study physician will be available.

3. Data Collection Period (Days 1-5)

Data Collection (before both control and experimental admissions)

A data collection period (5 days) will precede each of the control and experimental components of this study. All study subjects will be at home during these times. During the data collection period, subjects will be equipped with a DexCom Gen4 CGM. Subjects will be provided with instructions on how to upload CGM data through the DexCom software and how to download insulin pump data to record insulin pump information.

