At the end of the 5 day collection period, subjects randomized to the experimental session first will proceed as described in "Procedures During the Experimental Session." For those subjects who were randomized to the control session first, they will proceed as described in "Procedures During the Control Session." These two 40-hour periods will complete the 7 day study week (5 days data collection + 2 day experimental or control session). Selected subjects who are participating in the Substudy will follow "Procedures During the Substudy".

4. Procedures During the Experimental Session (Days 5-7)

EXPERIMENTAL SESSION DAY 5:

1. The study subject will perform a final upload of CGM, SMBG and insulin pump information on the evening prior to the session. If the subject is unable to do so then we will ask them to come earlier on the day of session (Day 5 of data collection period) for the study team to download the information at the office. If a subject does not provide the download until the day of session, a delay of up to 2 hours on the start time of the session may be required.
2. The subject will meet the study team and check in to the CDT Research House at 18:00.
3. The subject will be asked to perform a fingerstick using the study glucometer shortly after arrival. SMBG needs to be between 80-249 mg/dL prior to initiation of AAA control and glucose not expected to be <70 within two hours of initiation of AAA. AAA control may be delayed up to two hours until these conditions are met.
4. The study team will confirm that the subject brought his/her insulin, insulin pump supplies, and regular medications. The study team will also confirm the absence of a febrile illness and absence of acetaminophen use while wearing the CGM sensor. If all criteria are not met, the subject will be rescheduled.

5. Female subjects of childbearing potential will perform urine pregnancy test. If positive, the subject will discontinue study participation. The subject will be asked to seek confirmation of the test and the appropriate medical care.
6. The subject will be instructed that all fingersticks should be preceded by hand washing with warm water and a dry towel. The subject will be instructed to obtain fingerstick, avoiding alternative sites, when obtaining blood values. The first drop of blood will be discarded. The second hanging drop will be used to measure the glucose level.

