In the unlikely event of a disruption in 911 phone service, the Charlottesville-UVA-Albemarle Emergency Communications Center can be reached via their non-emergency number [contact]. This number feeds into their main call area where 911 dispatchers are available 24/7.

J. ENDPOINTS

This study is an early feasibility study that will test the efficacy of DiAs - a *smart-phone-based system* compared to CGM-enhanced insulin pump treatment in an outpatient setting. Specifically, the main study will have randomized cross-over design with each patient participating in two study weeks: 1) experimental involving 5 days of data collection followed by 2 days of AAA control using insulin pump and available CGM (however, treatment based on CGM will be discouraged) and 2) Control week involving 5 days of data collection followed by 2 structured days of study at home. This series of sessions will provide data for the regulatory approval of the AAA system and for its deployment in a longer-term trial of AAA at home. In addition, the data will be used to estimate the effect size of the AAA vs. CGM-enhanced insulin pump treatment in an outpatient setting.

The *basic unit for most analyses is the glucose trace of an individual*, i.e. a time-stamped series of CGM data recorded for each person. Summary characteristics and group-level analyses are derived after the individual traces are processed to produce meaningful individual markers of average glycemia and glucose variation. The following primary endpoints will be assessed:

- Risk for hypoglycemia as measured by the Low BG Index associated with exercise (SA1);
- Time spent within 70-180 mg/dl during the day (SA2);
- Risk for hypoglycemia overnight and time spent within the target range of 80-140 mg/dl overnight (SA3).

In addition, the following secondary endpoints will be assessed:

- Extent postprandial glucose excursions during the day;
- Overall number and extent of hypoglycemic episodes;
- System reliability, including failure rates of system components, frequency analysis of lost or inaccurate CGM records, percent time of active control, and inter-device connections between DiAs and the CGM and between DiAs and the insulin pump;
- System functionality, including the DiAs GUI in terms of patient comfort with operating the system, and
- The DiAs remote monitoring by medical personnel/technicians to confirm appropriate functioning outside of the hospital setting.

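### The main study is a randomised two-period cross-over, but the analysis plan names no period or sequence term and nothing protects balance between the sequences

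*Combined protocol and SAP*

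**What the plan says.** Section I.J states that "the main study will have randomized cross-over design with each patient participating in two study weeks". Order is allocated at random: section I.G.3 has "subjects randomized to the experimental session first will proceed as described in" one procedure, and those allocated to control first following another. No section gives the sequence ratio, blocking, or a rule for restoring balance when a subject is replaced.

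Section I.L contains the whole inferential plan: "Repeated measures ANOVA with contrasts will be used to compare the different study periods on the basis of these measures". It then sets out open- versus closed-loop for SA1, open-loop versus advisory control for SA2, and the overnight comparison for SA3. Model terms are not listed. The word periods in that sentence appears to mean clock windows and conditions, because the section opens by assigning a different time span to each aim. It does not read as first versus second period of a cross-over.

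Section I.G.3 also says "A data collection period (5 days) will precede each of the control and experimental components of this study". Section I.L gives these data no role in the main comparisons.

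On size, section I.C says "Thirty-six subjects with Type 1 Diabetes Mellitus will be needed to complete the protocol". It adds "With N=36 subjects, the power for proving SA1 is 97% and the power for SA3 is similar", gives a smaller figure of 85% for SA2, and states that "The significance level was reduced to $p=0.01$ to account for multiple comparisons".

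**The concern.** In a two-period cross-over, anything that differs between a subject's first and second week enters the within-subject difference, with opposite sign in the two sequences. If the model ignores order, that variation either sits in the error term or, with unequal sequences, leaks into the treatment estimate.

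The documents make such an effect plausible. The outpatient training visit is tied to the first study week (I.G.2), and some subjects are not proficient CGM users. Control-session meals must copy those of the experimental session (I.G.4 and I.G.5), although control may come first, so meal matching cannot work the same way in both sequences. The gap between sessions has a maximum of 4 weeks and no minimum (I.D).

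Section I.J says the results are meant to support regulatory approval and to estimate the effect size. A biased or needlessly imprecise contrast therefore matters even in an early feasibility study.

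**Working it through.** **Inputs from the documents.** N = 36 completers, alpha 0.01, powers of 97% (SA1, SA3 similar) and 85% (SA2) (I.C); effect size about 0.3 to 0.5 (I.K).

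**Assumptions.** Two-sided test; effect on the scale of the SD of the within-subject difference (dz); period effects k of 0.25 and 0.5 of that SD; sequence splits as shown. The documents give none of these.

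**1. The plan's own power.** For a paired t test, ncp = dz × √36 = 6 dz, df 35, critical t 2.724.
- dz 0.3: ncp 1.8, power about 20%.
- dz 0.5: ncp 3.0, power 61%.
- 85% needs dz 0.632; 97% needs dz 0.781.

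The stated powers cannot be verified, because no effect, SD or correlation is given per aim. This does not show them wrong. Read as Cohen's f with an assumed within-subject correlation of 0.5, f = dz/2, giving 0.32 and 0.39, inside 0.3 to 0.5.

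**2. Model.** D = δ + s·k + e, where D is experimental minus control, s = +1 for experimental first and −1 for control first, and SD(e) = 1.
- Order ignored: the mean of D estimates δ + k(n1−n2)/36. The expected sample variance is 1 + k² × 4·n1·n2/(36 × 35).
- Period term included: the estimate is the equally weighted average of the two sequence means, with variance (1/4)(1/n1 + 1/n2), df 34 and no bias.

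**3. Equal sequences, 18/18.** Bias is zero. The variance estimate becomes 1 + 0.0625 × 1.029 = 1.064 at k = 0.25, and 1 + 0.25 × 1.029 = 1.257 at k = 0.5. Power (simulation where k > 0 and the term is omitted):

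| True dz | k | Term omitted | Term included |
|---|---|---|---|
| 0.5 | 0 | 61.1% | 60.9% |
| 0.5 | 0.25 | 58% | 61% |
| 0.5 | 0.5 | 49% | 61% |
| 0.632 | 0.25 | 83% | 85% |
| 0.632 | 0.5 | about 76% | 85% |
| 0.781 | 0.5 | 94% | 97% |

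The test that omits the term is conservative here: type I error is about 0.4% at k = 0.5. With no period effect, including the term costs 0.1 to 0.2 points at dz 0.5 and 0.632, and less at 0.781.

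**4. Unequal sequences, term omitted.**

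| Split | k | Bias in SD | Type I error |
|---|---|---|---|
| 21/15 | 0.25 | 0.25 × 6/36 = 0.042 | 1.0% |
| 21/15 | 0.5 | 0.5 × 6/36 = 0.083 | 0.9% |
| 22/14 | 0.5 | 0.5 × 8/36 = 0.111 | 1.3% |
| 24/12 | 0.25 | 0.25 × 12/36 = 0.083 | 1.6% |
| 24/12 | 0.5 | 0.5 × 12/36 = 0.167 | about 3% |

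A bias of 0.083 is 17% of an effect of 0.5. With the term, type I error stays near 1%. The term costs more as balance worsens. With k = 0 and dz 0.5, the variance at 21/15 is (1/4)(1/21 + 1/15) = 0.0286 against 1/36 = 0.0278, and power is 59%; at 24/12 the variance is 0.0313 and power 55%. That is a reason to protect balance as well as to model it. If allocation were simple 1:1 randomisation (an assumption), a split of 21/15 or worse would have a chance of about 40%.

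**5. Pre-session CGM as covariate.** Only the difference between a subject's two baselines can help, because the cross-over already removes the subject's level. If it correlates ρ with the outcome difference, ncp = 3/√(1−ρ²), df 33. At dz 0.5 and 18/18, against 60.9% without it:
- ρ = 0: 60.8%
- ρ = 0.2: 63.0%
- ρ = 0.3: 66%
- ρ = 0.5: 76%

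**The case against.** **A reader might infer that the plan excludes a period term.** It does not. Section I.L lists no terms at all, and a repeated measures ANOVA can carry sequence as a between-subject factor, in which case the treatment-by-sequence interaction is the period effect. The defect is an omission to be specified.

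**A reader might infer that 20–30% attrition makes unequal sequences likely.** The figure in I.C includes screen failures, so it is not loss after randomisation. Thirty-six must complete, short sessions are rescheduled, and most stopped sessions can be repeated (I.I). What stands is narrower: nothing guarantees balance.

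**A period effect of 0.5 SD is large.** It equals the top of the hypothesised treatment effect on this scale, and no section supports that size. At 0.25 SD the loss at 18/18 is about 3 points. Training is also not confined to the first week: training on the control system is given in the experimental session whatever the order, subjects have at least 1 year of pump use, and five CGM days precede each session. These facts dampen a learning effect but do not rule it out.

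**A reader might infer that precision is thrown away by not using the pre-session CGM data.** This is not shown. The correlation is unknown. Home days lack the structured walk and meals, so it may be low, above all for the exercise-window endpoint of SA1. The second baseline also follows the first session. Averaging over all of Days 1–5 would do harm: check-in is at 18:00 on Day 5 and automated control starts at about 19:00, so treated hours would enter the covariate in the experimental week only.

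**Conclusion.** The point holds as an omission. Order is randomised, but the plan does not say that order is analysed. The consequence runs from negligible (no period effect) through about 3 points of power (0.25 SD, 18/18) to about 12 points (0.5 SD, 18/18), taking a paired effect of 0.5 SD. Material type I inflation appears only with marked imbalance together with a large period effect. The direction does not depend on how the protocol's effect size is read: with effects calibrated to its own 85% and 97%, omission still costs power at 18/18.

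The sizes rest on assumed period effects, splits and scale. No stated figure in the protocol is shown to be wrong by this point. The period term is the firm recommendation because it costs almost nothing when sequences are near equal. The baseline covariate is an option, and its absence is not a defect.

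**What to change.** In section I.L, state for each primary endpoint a linear mixed model with treatment, period and sequence as fixed effects and subject as random. A repeated measures ANOVA with sequence as a between-subject factor is an acceptable alternative, provided the treatment effect is the equally weighted average over the two sequences. The period term protects the treatment contrast; the sequence term mainly reflects carry-over or differences between the groups. The mixed model also keeps subjects with one usable session, in line with the plan's intention to use partial data.

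State the sequence ratio and how balance is kept when subjects are replaced.

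Optionally, pre-specify as covariate the same endpoint in the same clock window from the days before each session, using only hours before 18:00 on Day 5, in both weeks alike. State that its benefit is uncertain, least assured for SA1, and that the second baseline follows the first session.

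The cost is analysis-plan wording and modest programming. The CGM data are already collected.
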